## **I. Background**

Nonalcoholic fatty liver disease (NAFLD) is the most common cause of chronic liver disease in China now. It comprises a wide spectrum of disorders that range from simple steatosis to nonalcoholic steatohepatitis (NASH), advanced fibrosis, related cirrhosis, and even hepatocellular carcinoma (HCC). Currently there are no effective medications to cure NAFLD. Simple steatosis can progress into NASH, irreversible cirrhosis, and even HCC. Recently, extensive studies have emphasized that NAFLD is closely associated with metabolic syndrome, type 2 diabetes mellitus, dyslipidemia, insulin resistance, and oxidative stress/lipid peroxidation injury. In addition to the liver pathogenesis, both simple steatosis and NASH are well-established risk factors for many diseases, including diabetes, arteriosclerosis, hypertension, and colorectal cancer. Therefore, it is urgent to develop effective therapies for the early stages of NAFLD and thereby reduce the risk and morbidity of cirrhosis, HCC, diabetes, hypertension, colorectal cancer, and other serious diseases. Current treatments for NAFLD include weight reduction through lifestyle modification and exercise, insulin-sensitizing agents, lipid-lowering agents, and hepatoprotective drugs. (Cited from: Hu Yinxia, Li Lan, Yuan Yu, Wu Lihao, He Xingxiang. Therapeutic effect of teduglutide on non-alcoholic fatty liver disease in rats[J]. *World Chinese Journal of Digestology*, 2016 (7): 1009-1016.). However, the efficacy of these therapies is not satisfactory, some drugs may even induce liver toxicity. Thus, it is necessary to develop novel therapies that are effective and safe for the treatment of NAFLD.

The pathogenesis of NAFLD is complicated, which is mainly based on a 2-hit hypothesis, first proposed by Day and James in 1998. Essentially, the “first hit” refers to the development of hepatic steatosis via hepatic triglyceride accumulation and insulin resistance. The “second hit” is the shift from hepatic steatosis to NASH, including oxidative stress, inflammatory cytokines, and chronic intermittent hypoxia. Insulin resistance is the critical factor for hepatic steatosis. Insulin resistance is an abnormal metabolic state, in which peripheral tissue has impaired sensitivity to insulin

and attenuated biological response. In the stage of simple steatosis, improvement of insulin resistance could prevent the development of hepatic steatosis, reduce the accumulation of hepatic lipid, and effectively preclude the emergence of second hits. The liver and intestine are functionally connected in several ways. The interactions between the liver and the gut, called the "gut-liver axis," has been a gradually accepted theory and provides a powerful rationale for the treatment of many chronic liver diseases. Both animal experiments and clinical studies have demonstrated that the intestinal microflora are closely associated with the onset and progression of chronic liver diseases. Liver diseases can cause increased intestinal permeability, in which widened tight gap junctions lead to microbial translocation. On the other hand, microbial translocation and dysbiosis in the gut can further promote the development and progression of liver diseases. (Cited from: Chen Meihui, He Xingxiang, Cai Ji yi. Progress on liver dysfunction and small intestinal diseases[J]. Journal of Guangdong Pharmaceutical University, 2015, 31 (4): 558-560). A previous study found a NASH-like pattern of liver injury in a mouse model of small intestinal bacterial overgrowth (SIBO). Furthermore, the authors observed that SIBO mice had a higher incidence of NAFLD, which was related to hepatic steatosis. In the congenitally obese mice model, the intestinal mucosal barrier was damaged, which caused endotoxemia and led to the development of NASH via TNF-alpha secretion (cited from: Vanni E, Bugianesi E. The gut-liver axis in nonalcoholic fatty liver disease: Another pathway to insulin resistance, *Hepatology*, 2009, 49 (6): 1790-1792). Intestinal flora disorders and increased intestinal permeability were induced through immune responses, which furtherly promoted the development and progression of NAFLD. In contrast, the application of antibiotics, prebiotics and probiotics that regulate intestinal microbiota can prevent the progress of NAFLD (Cited from: Wang Junyao, Liu Yulan. The roles of gut-liver axison the development and progression of nonalcoholic fatty liver disease. *Journal of Clinical Hepatology*, 2012,15 (4): 276 -278). In addition, some studies reported that the changes in intestinal microbiota were significantly related to insulin resistance. Alterations in intestinal microbiota not only induced elevated lipopolysaccharides (LPS) in the intestinal tract, but also damaged the tight junctions

of the intestinal epithelium, leading to increased flow of LPS into the blood circulation, causing a series of non-specific inflammatory responses. In consequence, the alterations in intestinal microbiota interfered with insulin signaling and induced insulin resistance.

Some studies have shown that traditional Chinese medicine (TCM) has potentially effective therapies for chronic diseases. Additionally, TCM has unique therapeutic effects on some diseases that are particularly related to metabolic syndromes like hyperlipidemia, diabetes and fatty liver. For example, berberine was reported to improve insulin resistance, have glucose-and lipid-lowering effects, and was even used for the treatment of NAFLD. Researchers found in a NASH mice model that oral administration of berberine can change the intestinal microbiota, improve biochemical markers, attenuate liver histological changes, and reduce the intrahepatic inflammatory responses. The functions of berberine on whole-body energy metabolism and NAFLD were exerted by adjusting the ecological structure and microenvironment of the intestinal flora(Cited from: Cao Yi, Xu Leiming, PanQin, Wang Xiaoying, Shen Feng, Chen Guangyu, Fang Jianga. Modulation of gut microbiota with berberine improves nonalcoholic steatohepatitis in mice[J]. Journal of Clinical Hepatology, 2013, 16 (2): 137-140).Compound Zhenzhu Tiaozi capsules consist of eight Chinese herbal medications, such as Ligustrum lucidum, Atractylodes macrocephala, Radix Salviae Miltiorrhizae, pseudo-ginseng, Astragalus membranaceus. Previous studies found that Compound Zhenzhu Tiaozi capsules can reduce serum triglyceride (TG), total cholesterol (TC), fasting blood glucose, insulin, and the insulin resistance index. In addition, it can increase serum high-density lipoprotein cholesterol (HDL-C) levels, reduce weight, and improve obesity in a rat model, which means that it can be used to treat metabolic syndrome. It was also reported that Compound Zhenzhu Tiaozi capsules upregulated PI-3Kp85 mRNA expression in rat adipose tissue, which might be one of the mechanisms involved in insulin resistance (cited from: Hu Xuguang, Guo Jiao, Bai Weijian, He Wei, Wang Shou, Liu Shasha. Effect of Fufang Zhengzhu Tiaozi Capsules on Insulin Resistance and Insulin Signal PI-3K in Metabolic Syndrome Rats [J].Traditional Chinese Drug

Research and Clinical Pharmacology, 2012, 23 (2): 140-143). Additionally, Compound Zhenzhu Tiaozhi capsules can reduce serum TG, TC, and low-density lipoprotein cholesterol (LDL-C) and increase serum HDL-C levels in a hyperlipidemic rat model (Cited from: Tang Chunping, Gong Mengjuan, Guo Jiao, Yang Chaoyan, Chen Fangchao, Yao Hongxia, Chen Yuefeng. The effects of Fufang Zhenzhu Tiaozhi capsules on blood lipid level and hemorheology of rats with hyperlipemia [J]. Journal of Guangdong Pharmacy College, 2010, 26 (6): 612-616).

Based on the above studies, the investigators hypothesize that Compound Zhenzhu Tiaozhi capsules have the potential to effectively improve NAFLD and related biomedical markers. The possible mechanisms include the improvement of SIBO and the function of the intestinal mucosal barrier. The investigators thus designed the following clinical study to test this hypothesis.

## **II. Objectives**

To evaluate the efficacy of Compound Zhenzhu Tiaozhi capsules in the treatment of NAFLD and analyze the relationship between improvement in NAFLD parameters and changes in intestinal functions.

## **III. Content of the study**

1. To evaluate the relationship between the function of intestinal mucosal barrier, SIBO, and NAFLD;
2. To assess the effects of Compound Zhenzhu Tiaozhi capsules on intrahepatic fat content, hepatic noninvasive score, liver biochemical parameters, blood lipid, and insulin resistance. To evaluate the therapeutic effects of Compound Zhenzhu Tiaozhi capsules on the treatment of NAFLD, and determine whether the risk stratification of atherosclerotic cardiovascular disease (ASCVD) and quality of life (using the 36-Item Short Form Health Survey [SF-36]) can be improved in NAFLD patients with Compound Zhenzhu Tiaozhi capsules.
3. To compare the therapeutic effects of Compound Zhenzhu Tiaozhi capsules with conventional medications in the treatment of NAFLD, and to compare their efficacies in improving the risk stratification of ASCVD and quality of life, as

assessed by the SF-36.

4. Finally, to analyze the relationship of Compound Zhenzhu Tiaozi capsules in improving NAFLD and parameters related to the function of the intestinal mucosal barrier and SIBO.

#### **IV. Methods**

This is an interventional and randomized parallel control study. The study will be conducted from December 31 2017 to December 31 2019. The recruitment and observation period will start in December, 2017 and continue until the required sample size is reached. Research venue: First Affiliated Hospital, Guangdong Pharmaceutical University, Guangdong province, China. Institute level: a third-grade-A-class hospital.

1. Ethical approval: The study will be conducted after obtaining ethical approval from Ethics Committee of the First Affiliated Hospital, Guangdong Pharmaceutical University. The investigators will inform all prospective subjects of the study background, purpose, design, and medication contents. If a subject is willing to participate in the study, he or she will sign the consent form (Supplementary 1).

#### 2. Enrollment:

The subjects will be enrolled following the design of a prospective study. The inclusion criteria will be strictly in accordance with the diagnostic criteria of simple steatosis and NASH, as stipulated in the *Chinese Guidelines for the Diagnosis and Treatment of Nonalcoholic Fatty Liver Disease (Revised version 2010)*. The subjects should have a diagnosis of simple steatosis or NASH (age distribution: 18 to 75 years old), with serum alanine transaminase (ALT)  $\leq 2$  times the upper limit of normal, with no other chronic liver diseases or serious complications in other organs, with no malignant tumors.

2.1. Diagnostic Criteria of NAFLD (2010): NAFLD can be diagnosed if the following items 1–4, plus item 5 or item 6 are present:

- i. No alcoholic history (alcohol consumption  $< 140$  g/week for male; or  $< 70$

g/week for female);

- ii. No other diseases that can lead to fatty liver, such as viral hepatitis, drug-induced liver disease, total parenteral nutrition, hepatolenticular degeneration diseases, or autoimmune liver diseases;
- iii. Overweight and/or visceral obesity, hyperglycemia, dyslipidemia, hypertension and other metabolic syndrome;  
Serum transaminase and GGT levels are normal or elevated to a mild to moderate degree;
- iv. Liver imaging findings show diffuse hepatic steatosis;
- v. A liver biopsy meets the histologic diagnostic criteria of fatty liver diseases;

2.2. Diagnostic criteria of simple steatosis: Simple steatosis can be diagnosed if the following item 1-2, plus item 3 or item 4 are present.

- i. Presence of item 1-3 of the clinical diagnosis criteria of NAFLD;
- ii. Liver biochemical tests are normal (blood biochemical analysis);
- iii. Liver imaging findings meet the diagnostic criteria for hepatic steatosis (Fibro touch test);
- iv. A liver biopsy meets the histologic diagnostic criteria for simple hepatic steatosis.

2.3. The diagnostic criteria of NASH: NASH can be diagnosed with the following items 1 to 3 or item 4.

- i. Presence of items 1–3 of the clinical diagnosis criteria of NAFLD;
- ii. Serum ALT levels are persistently elevated for more than 4 weeks;
- iii. Liver imaging findings show diffuse hepatic steatosis;
- iv. A liver biopsy meets the histologic diagnostic criteria for NASH.

2.4. The following individuals will be considered as lost to follow-up: first, patients who suddenly present serious physical or mental diseases (not related to the study) during the study period, such as malignant tumors, severe mental illness, traffic accidents, etc.; second, patients who have serious side effects in which the symptoms can be relieved by discontinuing the study medication; third, patients who actively ask to stop using the study medication or refuse to come to follow up visits. Fourth,

patients who need to take other medications due to the development of other new diseases, where the new medications may interfere with the study results, such as hypoglycemic agents, including insulin.

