### 3. Assignment and intervention:

#### 3.1. Calculation of the sample size and the method of assignment:

Sample size calculation: A total of 196 patients will be enrolled in this study. The sample size is estimated as follows:

Previous studies have reported that the efficiency rate of metformin and simvastatin in the treatment of NAFLD is 36-52%. The investigators hypothesize that the efficiency rate of Compound Zhenshu Tiaozhi capsules will increase by 25% compared to standard drugs.

Statistical calculation:  $P_1 = 69\%$ ,  $P_2 = P_3 = 44\%$ ,  $P_4 = 10\%$ ,  $\delta = P_1 - P_2 = 25\%$ , with  $\alpha = 0.05$ , power = 0.80, and a bilateral test, of which  $w = \sqrt{\frac{\sum_{i=1}^m (P_{t,i} - P_{c,i})^2}{P_{c,i}}}$ , thus n will be equal to 44. Assuming that the rate of loss to follow up is 10%, each group will require 49 cases. Therefore, a total of 196 cases will be required for the four groups.

3.2 The method of assignment: [name], a staff member working in the Department of Statistics in Guangdong Pharmaceutical University, is responsible for generating random sequences using the SAS software. A total of 196 numbers from 1 to 196 will be randomly generated (Supplement 2). Newly diagnosed patients who meet the inclusion criteria will have a case number according to their order of enrollment (for example: case number of the first patient: 001, second patient: 002). They will then obtain the corresponding therapeutic regimens based on their case number with 1:1:1:1 ratio randomized tables. The first group is the TLC group; the second group is the TLC + metformin group (0.5 g, PO tid); the third group is the TLC + Compound Zhenzhu Tiaozhi capsules group (2.52 (four tablets), PO tid); the fourth group is the TLC + simvastatin group (20 mg, PO qn).

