3.4 Sample Size

A total of 196 patients will be enrolled in this study. The sample size is estimated as follows:

Previous studies have reported that the efficiency rate of metformin and simvastatin in the treatment of NAFLD is 36-52%. We hypothesize that the efficiency rate of Compound Zhenshu Tiaozhi capsules will increase by 25% compared to standard drugs.

Statistical calculation: $P_1 = 69\%$, $P_2 = P_3 = 44\%$, $P_4 = 10\%$, $\delta = P_1 - P_2 = 25\%$, with $\alpha = 0.05$,

power = 0.80, and a bilateral test, $n = \frac{\chi_{\alpha}^2 + \chi_{\beta}^2}{w^2}$, of which $w = \sqrt{\sum_{i=1}^m \frac{(P_{t,i} - P_{c,i})^2}{P_{c,i}}}$, thus n will be equal to 44.

Assuming that the rate of loss to follow up is 10%, each group will require 49 cases. Therefore, a total of 196 cases will be required for the four groups.

4. Evaluation of the Efficacy of Parameters and Predictors

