6.2 Per Protocol Set (PPS)

The PPS refers to the set of subjects who meet the inclusion criteria and complete the research project, which also means they comply with the research protocol, have good compliance, do not use banned substances during trial, and have completed the case report form (CRF). The PPS analysis is mainly used to assess primary efficacy.

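### Patients who stop study drug or need interfering medication are classed as lost to follow-up and, because the per-protocol set is the main efficacy set, leave the primary result for treatment-related reasons that differ by arm

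*Protocol*

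**What the plan says.** Protocol section IV.2.4 opens with "The following individuals will be considered as lost to follow-up" and lists four groups:

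1. Patients with a serious illness or injury unrelated to the study.
2. "patients who have serious side effects in which the symptoms can be relieved by discontinuing the study medication".
3. "patients who actively ask to stop using the study medication or refuse to come to follow up visits".
4. "patients who need to take other medications due to the development of other new diseases, where the new medications may interfere with the study results", with hypoglycaemic agents, including insulin, as the example.

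The primary endpoint (Protocol 4.1, SAP 4.1) is a drop of at least one grade in the fat attenuation index, which is measured at months 0, 1, 3 and 6.

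The SAP sets out the analysis in four places:

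- **6.1** keeps dropouts (its 'shedding cases') in the full analysis set (FAS) and refers to intention to treat when the primary outcome is missing.
- **6.2** restricts the per-protocol set (PPS) to eligible, compliant completers who used no banned substances, and adds: "The PPS analysis is mainly used to assess primary efficacy".
- **6.3** puts in the safety set randomised patients with at least one dose and at least one safety assessment.
- **9.3** permits earlier results to be carried forward in four situations.

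On sample size, SAP 3.4 and Protocol 3.1 say: "Assuming that the rate of loss to follow up is 10%, each group will require 49 cases".

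**The concern.** Loss to follow-up ordinarily means that the outcome could not be obtained. Of the four groups, only the patients who refuse visits clearly fit that meaning. A patient who stops a capsule because of a side effect, or who starts another drug for a new disease, can usually still have a scan at month 6. Neither document says whether such patients keep attending.

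The label matters because of the analysis set it leads to. Someone counted as lost has not completed the study and so falls outside the PPS, the main set for primary efficacy. The reasons for leaving are tied to treatment:

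- Side effects depend on the drug.
- The trial is open-label (SAP 2.1 and 3.1), so a request to stop can depend on knowing the arm.
- The TLC-only arm has no study drug, so group 2 and the stop-medication half of group 3 cannot arise there.

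The main comparison would then be between patients selected differently in each arm, and randomisation would no longer protect it. Safety information after discontinuation could also go uncollected.

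**Working it through.** **The plan's own figure.** The inputs are 44 evaluable patients per group ("thus n will be equal to 44") and a 10% allowance. 44/(1 − 0.10) = 48.9, rounded up to 49, and 49 × 4 = 196. This matches "a total of 196 cases will be required for the four groups". The allowance arithmetic is right.

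**Tracing the groups through the plan.**

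| Patient | Could still be scanned? | In PPS (main)? | In FAS? |
|---|---|---|---|
| Unrelated serious illness | Sometimes | No | Yes, as a dropout |
| Stops for side effects | Usually | No | Yes, as a dropout |
| Asks to stop drug | Usually | No | Yes, as a dropout |
| Refuses visits | No | No | Yes, as a dropout |
| Interfering drug for new disease | Usually | No | Yes, as a dropout |

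The second column is judgement; the documents are silent. The others follow from Protocol 2.4 with SAP 6.1 and 6.2, taking a patient counted as lost to be a dropout.

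**What carry-forward covers (SAP 9.3).** Rule 1 covers a missing month 6 value with no response when therapy ceased. Rule 2 covers withdrawal without a response. Rule 3 covers a missed intermediate scan. Rule 4 covers withdrawal after full recovery. A patient who has dropped one grade, has not fully recovered, stops drug and has no month 6 scan fits none of them. All four rules say that results can be carried forward, not that they will be.

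**Illustration in one arm (assumed numbers).** Take 49 randomised, 5 of whom stop, with 30 responders among the other 44. Let k be the number of responders among the 5.

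PPS rate = 30/44 = 68.2%, whatever k is. All-randomised rate = (30 + k)/49.

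| k | All randomised | PPS minus all randomised |
|---|---|---|
| 0 | 30/49 = 61.2% | +7.0 points |
| 3 | 33/49 = 67.3% | +0.8 |
| 4 | 34/49 = 69.4% | −1.2 |
| 5 | 35/49 = 71.4% | −3.2 |

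The k = 0 gap is 7.0/25 = 28% of the planned 25-point difference.

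**At the planning rates.** If a fraction d of an arm is excluded and all of those are non-responders, a true rate p appears as p/(1 − d).

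| d | p = 44% | p = 69% |
|---|---|---|
| 5% | 46.3% | 72.6% |
| 10% | 48.9% | 76.7% |
| 20% | 55.0% | 86.3% |

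If two arms both truly respond at 44% and only one loses 10% this way, a false difference of 48.9 − 44 = 4.9 points appears. If instead the excluded 10% were all responders, the 44% arm would show (0.44 − 0.10)/0.90 = 37.8%, a bias the other way.

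**The case against.** The best defence is that section 2.4 only applies a label. It does not say that visits stop, that data are deleted or that anyone leaves the analysis. A reader might infer from it that outcomes are discarded, and the documents do not support that: SAP 6.1 keeps dropouts in the FAS. In the k = 0 illustration, rules 1 and 2 of SAP 9.3 allow the five to be carried forward as non-responders, so the FAS can give 61%; the 68% arises only in the PPS. This stands. The exclusion comes from section 2.4 combined with SAP 6.2, not from section 2.4 alone.

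A reader might also infer that the 10% allowance is too small because it was meant for true loss only. That does not follow. Section 2.4 defines loss to follow-up to include all four groups, so the 10% may cover them all, and the inflation reproduces. What can be said is that the figure has no source and does not separate true loss from discontinuation.

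Nor do the documents show that safety data on these patients are lost in general. Under SAP 6.3 a dosed patient with one safety assessment who stops for a side effect stays in the denominator, and the event that led to stopping can be counted. Only information after stopping is in doubt.

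Finally, group 4 is narrower than any new medicine: it requires a new disease and a drug that may interfere with the results. Because that drug might itself alter liver fat, the direction of bias cannot be assumed.

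What survives is that the FAS is not the main analysis, and that the carry-forward rules are optional and leave a gap.

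**Conclusion.** The concern holds in this form: the protocol merges stopping treatment with loss of outcome, and the SAP then makes a completer set the main efficacy set. Followed as written, the plan removes patients from the primary result for treatment-related reasons that cannot be the same in all four arms.

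The size is not known, because the documents give no discontinuation rate. With 5 of 49 excluded and 30 responders among the rest, the bias in one arm runs from +7.0 to −3.2 points, depending on how many of the 5 responded. The upper end assumes that none did. The conclusion that selection is non-random and unequal by arm does not depend on these numbers; the size and direction do.

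**What to change.** Change both documents together. Amending the protocol alone would leave these patients outside the main efficacy set.

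- **Protocol 2.4.** Split it into two definitions. The first is patients who stopped study medication or started interfering medication, with unrelated serious illness placed here whenever the patient can still attend. The second, lost to follow-up, is only those from whom no outcome can be obtained.
- **Visits.** State that the first group keeps the month 1, 3 and 6 fat attenuation and safety assessments and is analysed in the randomised arm.
- **SAP 6.2.** Make the FAS the main set for primary efficacy, with the PPS as supportive.
- **SAP 9.3.** Make the missing-data rules definite, and cover the patient who has responded without full recovery, stops drug and has no month 6 scan.
- **SAP 3.4 and Protocol 3.1.** Give the source of the 10% and say which groups it covers.

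The rules on when treatment stops are untouched. If all randomised patients are followed and the 10% then means true loss only, the total stays at 196. The cost is wording, plus some visits by patients off study drug at time points already scheduled.
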